Protocol Clinical Trial

**Effect of cryoablation of intercostal nerves on
pain in the early postoperative period in
patients with minimally invasive mitral valve
surgery: a pilot prospective randomized
study (BLOCK trial).**

NCT number: NCT06443931

Date: 05.04.2024

Background

Cardiovascular diseases are one of the main causes of death worldwide. According to pathological studies, heart defects occur in 4-7% of cases, and the most common defect among the defects is damage to the mitral valve [1]. Significant advances in surgical practice, instrumentation, tissue manipulation, and perfusion technology have made it possible to perform mitral valve surgery using mini-approaches. Minimally invasive mitral valve surgery has become the standard of care in some specialized cardiac centers around the world due to its excellent results, even despite longer cardiopulmonary bypass times and aortic occlusion. In 2008, P. Modi and co-authors, a meta-analysis has been published in which the authors come to the conclusion that a minimally invasive approach for correcting mitral valve pathology actually has significant advantages: early activation of patients, shorter duration of stay in the recovery room, shorter wound healing times, advantages in case of repeated interventions, less the number of bleedings and purulent-septic complications compared to classical sternotomy [2]. But despite all the advantages of this approach, severe pain after minimally invasive cardiac surgery continues to remain a serious problem [3]. Acute pain occurs after dissection of the chest, pleura and pericardium, compression of the intercostal nerve with a retractor, as well as dissection of the intercostal and pectoral muscles during surgical access. It limits breathing and cough in the postoperative period, which can subsequently lead to hypoxemia, sputum stagnation, atelectasis, pneumonia, myocardial ischemia, slow recovery, and also an increase in the length of hospitalization [4]. Therefore, additional emphasis and attention is paid to protocols for early functional restoration and pain reduction for this group of patients. There are protocols for “enhanced recovery after surgery” (ERAS - Enhanced Recovery After Surgery), their use makes it possible to achieve shorter stays in the intensive care unit, reduce hospitalization, improve treatment outcomes and reduce financial costs. One of the components of ERAS is the use of additional pain management modalities [5]. However, in cardiac surgery, traditional methods of regional anesthesia, such as thoracic epidural anesthesia or paravertebral block, are not usually used due to intraoperative heparinization and the associated higher risk of spinal or epidural hematoma. Finding an optimal and effective pain management strategy for this category of patients remains an unsolved problem today.

Intercostal nerve cryoablation is considered a relatively new treatment for postoperative pain in patients undergoing minimally invasive mitral valve surgery. One of the first studies of cryoneurolysis was conducted back in 1974 in thoracic surgery [9]. In 76 patients, the use of intercostal cryoablation resulted in a significant reduction in postoperative opioid analgesic consumption. These results were subsequently confirmed in several other studies and the data were retrospective. In 2000, a prospective randomized controlled trial was published involving 30 patients who underwent minimally invasive mitral valve surgery or minimally invasive coronary artery bypass grafting and underwent intercostal

cryoablation. According to the results, a decrease in postoperative pain syndrome was observed, and less painkillers were required [10].

In the study O'Connor LA et al. in patients undergoing surgical stabilization of the ribs, cryoablation of the intercostal nerves resulted in a 25% reduction in opioid analgesics consumption compared with patients who received an extrapleural catheter, and pain scores were reduced by 22% in the cryoablation group [7]. Similar results (cryoablation made it possible to significantly reduce morphine consumption compared to the control group and reduce pain) were also described in recent retrospective studies through 2023 in other patient groups: patients who have undergone pulmonary resection using single-port thoracic video-assisted access, where cryoablation was used as a method of postoperative pain relief [8] and patients undergoing lung transplantation [12].

In the FROST study for 2021 the use of this method in patients with lateral thoracotomy showed significant improvement in spirometry parameters (FEV1, FVC) after 48 hours, as well as 30 and 60 days after surgery [6]. Studying the influence of pain was not the main objective of this work; pain was assessed using VAS and did not show a difference. However, improvement in breathing parameters in the early postoperative period may indirectly be associated with a lower level of pain and a more comfortable state of the patient; the consumption of opioid analgesics was not properly assessed in this study.

In 2021 Peter I Cha and others published a systematic review of 23 studies on the effectiveness of intercostal cryoneurolysis in patients with pectus excavatum, lateral thoracotomy, post-thoracotomy pain syndrome, traumatic rib fracture and chest wall malignancy. Most studies have demonstrated a reduction in opioid analgesic use with intercostal nerve cryoablation compared with traditional pain management techniques. In patients requiring lateral thoracotomy, intercostal cryoablation results in decreased opioid analgesic dosage (grade 2A) and improved pain scores (grade 2C) postoperatively (PICO guidelines) [11].

Finding an effective and at the same time simple strategy for pain relief in the early postoperative period in patients undergoing minimally invasive mitral valve surgery is an urgent task; it is advisable to conduct a prospective clinical study with a well-thought-out design in this direction.

Study design

A single-center pilot prospective randomized clinical trial is planned, with a 1:1 allocation ratio.

Objectives

To determine whether cryoablation of intercostal nerves provides a clinically significant analgesic effect, which is reflected in a decrease in opioid analgesics consumption and in a decrease in pain according to VAS in patients undergoing minimally invasive mitral valve surgery. To obtain preliminary data for planning a subsequent larger prospective randomized trial.

Research aims:

1. Conduct a comparative analysis of the data on the opioid analgesic consumption necessary for pain relief when using cryoablation of intercostal nerves and the standard treatment protocol in patients with minimally invasive mitral valve surgery.
2. To conduct a comparative assessment of pain syndrome according to VAS in patients in the intercostal nerve cryoablation groups and the standard treatment protocol in patients with minimally invasive mitral valve surgery.
3. Assess spirometry parameters (FEV1, FVC) before surgery, 48 hours after surgery and before discharge when using cryoablation of intercostal nerves and the standard treatment protocol in patients with minimally invasive mitral valve surgery.
4. To evaluate the incidence of side effects and the need for inotropic and vasopressor support in the early postoperative period in the intercostal nerve cryoablation and standard treatment protocol groups in patients undergoing minimally invasive mitral valve surgery.
5. To evaluate the duration of mechanical ventilation in the postoperative period when using cryoablation of intercostal nerves and the standard treatment protocol in patients with minimally invasive mitral valve surgery.
6. Assess the length of stay in the ICU and the duration of hospitalization when using cryoablation of intercostal nerves and the standard treatment protocol.
7. Assess the presence of chronic post-thoracotomy pain syndrome in the postoperative period after 2 and 6 months and the presence of side effects after cryoablation of intercostal nerves (paresthesia in the area of surgical access and in the right arm).

Research participants

30 patients (15 patients in each group) who are scheduled to undergo minimally invasive mitral valve surgery under cardiopulmonary bypass.

Inclusion criteria

- Written informed consent;

- Minimally invasive mitral valve surgery.

Non-inclusion criteria:

- patient refusal;
- pregnancy;
- treatment with antidepressants or epileptic drugs;
- depression, which can significantly affect the perception of pain;
- chronic use of analgesics;
- participation in competing randomized clinical trials.

Exclusion criteria:

- Extended mechanical ventilation, more than 12 hours.

Randomization, allocation, blinding

A block will be used to distribute participants into groups randomization with block lengths of 2 and 4. Masking will be performed for the statistician. Sample size calculation was not performed because no data were available to estimate sample size.

Description and rationale for the route of administration, dosage, dosage regimen and course of treatment

Patients undergoing minimally invasive mitral valve surgery while on cardiopulmonary bypass will be randomized into two groups:

1. Patients receiving cryoablation of intercostal nerves (CryoINB) as a method of pain relief.
2. Patients who will undergo a standard pain management protocol.

Patients in the CryoINB group will undergo cryoablation of the intercostal nerves, at the end of surgery before weaning from CPB, using the «ArtiCue» device for 120 seconds at a temperature of -50°C to -70°C, in the intercostal spaces where the surgical approach is located, one intercostal space above and one below it. Cold leads to axonotmesis, in which the axon and myelin sheath are damaged, preventing the pain signal from traveling along the sensory nerve. However, the structural elements of the nerve are preserved, which promotes complete regeneration at a rate of 1–2 mm per day, thereby restoring normal function within several months.

Patients in the group with the standard anesthesia protocol will receive an intercostal block in the area of surgical access - a single injection of 0.75% ropivacaine solution 20 ml. A local anesthetic will be injected into the area of the posterior wall of the chest 2 cm lateral to the sympathetic trunk under the parietal pleura in the intercostal space along the intercostal nerve, where the surgical approach is located [14].

All study participants will receive postoperative pain management according to the protocol described below:

If VAS >4 points on the scale, patients will receive NSAIDs (paracetamol 1 g IV) [15, 16]. The maximum daily dose will be 4 g/day.

If there is no effect after 30 minutes, opioid analgesics will be administered (MORPHINE 10 mg). The maximum daily dose of opioids for adults will be 50 mg.

If other opioid analgesics are administered, they will be converted to morphine equivalent (MME) [13].

Drug	Conversion factor to morphine	Conversion factor from morphine	Equianalgesic dose	
			IM/IV (mg)	PO (mg)
Morphine	1	1	10	30
Hydromorphone	×5	1/5	1.5	7.5
Oxycodone	×1.5	1/1.5	—	20
Hydrocodone	×1	×1	—	30
Fentanyl	×100	1/100	—	0.1
Codeine	/10	×10	130	200
Nalbuphine	×1	×1	—	—
Oxymorphone	×3	1/3	1	10
Tapentadol	×1	×1	—	—
Tramadol	/10	×10	100	120
Buprenorphine	×10	1/10	0.3	0.4 (SL)
Meperidine	/10	×10	100	300
Methadone	— ^a	— ^a	1	2

(Dott D., Sobey CM Common Opioids //Hospitalized Chronic Pain Patient: A Multidisciplinary Treatment Guide. – 2022. – P. 151.)

Primary outcome:

The opioid analgesic consumption within 48 hours after surgery, calculated in milligram morphine equivalent (MME).

Secondary endpoints:

- The intensity of pain, assessed using a visual analogue scale (VAS) after extubation, 6, 12, 24, 36, 48 hours after surgery
- Dynamics of spirography (FEV1, FVC) before surgery, 48 hours after surgery, before the patient's discharge
- Frequency of side effects (nausea, vomiting, etc.)
- Need for inotropic/vasopressor support
- Duration of mechanical ventilation
- Duration of ICU stay
- Duration of hospital stay
- Follow-up after 2 and 6 months (CPPS, numbness in the right arm and in the area of surgical access)

Statistical analysis

Comparisons of continuous outcomes will be made using the Mann-Whitney test for non-normal variables and the Welsh t test for normal variables. Comparisons of binary outcomes will be made by the chi-square test or Fisher's exact test.

Data processing

All information will be collected by staff using paper documentation, the data of which will then be entered into an electronic database.

Initial data

1. Demographic indicators: age, gender, height, weight, body mass index.
2. Disease severity: left ventricular ejection fraction, left ventricular EDV, presence of mitral regurgitation, degree of mitral regurgitation, peak mitral valve gradient, pulmonary artery pressure, FAC (Fractional Area Change), history of cardiac surgery, NYHA class, EuroSCORE II risk.
3. Concomitant diseases: myocardial infarction, arterial hypertension, diabetes mellitus, atrial fibrillation, ventricular extrasystole, COPD, chronic kidney disease, stroke, epilepsy.
4. Taking the following medications: antidepressants, antiepileptic drugs, long-term use of NSAIDs (more than 14 days), opioid analgesics.

During the operation:

1. Type of surgery (mitral valve repair or replacement).
2. Time of heart-lung bypass (minutes).
3. Aortic occlusion time (minutes).
4. Minimum temperature during surgery.
5. Dose of fentanyl per operation (mg/kg).
6. Inotropic index.

Period of hospitalization and stay in the ICU:

1. Dose of opioid analgesics 48 hours after surgery (morphine in MME).
2. Assessment of pain intensity using a visual analogue scale (VAS) after extubation, 6, 12, 24, 36, 48 hours after surgery.
3. Duration of mechanical ventilation (in days).
4. The presence of side effects (nausea, vomiting).
5. Need for inotropic and vasopressor support, VIS.
6. Surgery complications (pulmonary edema, bleeding, febrile seizures, heart failure, respiratory failure, myocardial infarction).
7. Duration of stay in the ICU (in days).
8. Duration of hospitalization (in days).
9. The result of spirometry before surgery, 48 hours after surgery and before

discharge.

Ethical issues

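### Excluding patients ventilated for more than 12 hours acts after treatment, on a variable that is itself an aim and a secondary endpoint

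*Protocol*

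**What the plan says.** The protocol has two separate lists. Non-inclusion criteria holds items known before surgery, such as refusal, pregnancy and chronic analgesic use. Exclusion criteria holds one item: "Extended mechanical ventilation, more than 12 hours".

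The same variable is an outcome. Research aims, item 5, reads "To evaluate the duration of mechanical ventilation in the postoperative period when using cryoablation of intercostal nerves" and goes on to name the standard-protocol comparator. Secondary endpoints lists "Duration of mechanical ventilation".

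Cryoablation is performed "at the end of surgery before weaning from CPB". The primary outcome is opioid use in the 48 h after surgery, in MME. On blinding, the protocol says only "Masking will be performed for the statistician". Statistical analysis names the tests. It does not say whether a patient excluded under the 12 h rule is followed up, analysed or replaced.

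**The concern.** An exclusion rule should rest on something known before allocation, or at least on something the treatment cannot affect. This one rests on a postoperative variable that the trial sets out to compare between arms. Two things are at stake if excluded patients leave the analysis.

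- **Ventilation time** is compared only among values of 12 h or less. The arm with longer ventilation loses more of its upper tail, so a true difference shrinks.
- **The primary outcome** is no longer compared between the groups as randomised. It is biased if exclusion differs between arms and ventilation time is related to opioid use.

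Unequal exclusion is plausible, though not shown. Only the statistician is stated to be masked, so those deciding on extubation may know the arm. The Background says of acute pain: "It limits breathing and cough in the postoperative period, which can subsequently lead to hypoxemia". The trial is also meant to supply preliminary data for a larger one, and distorted estimates would carry over.

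**Working it through.** **Order of events.** Study treatment is given during the operation, so allocation precedes it (the time of randomisation is not stated; this is inferred). Postoperative ventilation beyond 12 h is known only later, and inside the 48 h primary window. The rule therefore cannot act as an entry criterion.

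**Inputs.** From the protocol: 15 patients per arm, cut-off 12 h. It gives no ventilation times, exclusion rate or SD, so there is no figure to reproduce. Assumed: log-normal ventilation time with log-SD s = 0.4–0.6; control v cryo medians of 6 v 4.5, 8 v 6 and 10 v 7 h; MME SD 20; correlation ρ between MME and log ventilation time of 0.2 or 0.5.

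**Formulas.** With median m and a = ln(12/m)/s:

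- share excluded = 1 − Φ(a)
- mean without the rule = m·exp(s²/2)
- mean among those at 12 h or less = m·exp(s²/2)·Φ(a − s)/Φ(a)
- MME shift with no true opioid effect = 20·ρ·[φ(a)/Φ(a) in control − φ(a)/Φ(a) in cryo]

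**One case in full (8 v 6 h, s = 0.5).** a = ln(12/8)/0.5 = 0.811 in control and ln(12/6)/0.5 = 1.386 in cryo. Excluded: 20.9% v 8.3%. Means without the rule: 9.07 v 6.80 h, difference 2.27 h. Means with it: 7.13 v 6.02 h, difference 1.11 h. Share lost: 1 − 1.11/2.27 = 51%. MME shift at ρ = 0.5: 20 × 0.5 × (0.363 − 0.166) = 2.0.

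**All cases** (ranges over s = 0.4–0.6):

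| Control v cryo median | Excluded, control v cryo | Mean difference, full → cut off | Mean difference lost | Median difference lost | Mann-Whitney effect lost | MME shift, ρ = 0.5 |
|---|---|---|---|---|---|---|
| 6 v 4.5 h | 4–12% v 1–5% | 1.62–1.80 → 1.35–1.00 h | 17–44% | 7–24% | 4–13% | 0.7–1.2 |
| 8 v 6 h | 16–25% v 4–12% | 2.17–2.39 → 1.33–0.94 h | 39–61% | 24–43% | 13–22% | 1.9–2.0 |
| 10 v 7 h | 32–38% v 9–19% | 3.25–3.59 → 1.48–1.07 h | 55–70% | 41–55% | 21–28% | 2.9–3.6 |

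The Mann-Whitney effect is P(control > cryo), measured from 0.5. At 6 v 4.5 h and s = 0.4, for example, it falls from 0.694 to 0.686.

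At ρ = 0.2 the MME shift is 0.3–1.4 over all three pairs. A positive ρ makes cryoablation look worse, a negative one better. Equal medians give a shift of 0. For scale, the standard error of the difference is 20·√(2/15) = 7.3 MME, so the largest shift is 3.6/7.3 = 0.49 of it.

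**Will the rule be used?** If 5% or 10% of patients exceed 12 h, the expected number excluded is 30 × 0.05 = 1.5 or 30 × 0.10 = 3. The chance of at least one is 1 − 0.95³⁰ = 79% or 1 − 0.90³⁰ = 96%.

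**Does the rule secure complete VAS data?** No. Pain is scored as follows: "The intensity of pain, assessed using a visual analogue scale (VAS) after extubation, 6, 12, 24, 36, 48 hours after surgery". A patient ventilated for 6–12 h stays in and cannot be scored at 6 h. At medians of 4.5–8 h, 23–72% of the retained patients are still ventilated then.

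**The case against.** The protocol does not say that excluded patients leave the analysis, and an SAP that is not shown could keep them. That stands, and it is why the consequence is stated conditionally. It does not rescue the rule: the protocol itself labels these patients excluded, on a variable it also compares.

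The loss of mean difference overstates the damage. The protocol assigns Mann-Whitney to non-normal variables, and on that scale the loss is 4–28%, not 17–70%. This is correct, and it lowers the practical size. Some loss remains in every case examined.

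The largest figures come from the 10 v 7 h pair, where about 6.2–8.5 of 30 patients would be excluded, well above the 5–10% used for the chance of any exclusion. At 6 v 4.5 h the primary shift at ρ = 0.5 is only 0.10–0.17 of a standard error. This also stands.

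All three pairs assume that cryoablation shortens ventilation by 25–30%. The protocol states no such effect, the control arm has an active intercostal block, and the protocol reports that one cited trial of cryoablation found no VAS difference. So unequal exclusion is a possibility, not an expectation.

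Finally, the rule may have a purpose. Rescue analgesia is triggered by pain score ("If VAS >4 points on the scale, patients will receive NSAIDs"), which cannot be obtained during ventilation, so long-ventilated patients blur the meaning of 48 h opioid use. That is a fair reason to report opioids before and after extubation separately. It is not a reason to remove randomised patients.

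**Conclusion.** The concern holds, and the rule must be corrected. A stated exclusion criterion acts after treatment on a variable that is also an aim and a secondary endpoint. If it is applied to the analysis, cutting off the ventilation endpoint follows directly, and any true difference is attenuated by the shares tabulated above under the stated log-normal assumptions. The effect on the primary outcome is smaller and less certain: at most about half a standard error in the most extreme case, much less in milder ones, and zero in this model if exclusion is alike in both arms. Even so, the primary comparison would no longer be the randomised one. With 15 per arm each removal costs 1/15, about 7%, of a group, and the data cannot be recovered if follow-up stops at exclusion.

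**What to change.** State that ventilation beyond 12 h does not remove a randomised patient from follow-up or analysis. Analyse all randomised and operated patients as allocated for the primary outcome, ventilation time and every other outcome. Report the number over 12 h in each arm, and keep the subset of 12 h or less as a labelled sensitivity analysis.

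Three additions help, though the point does not depend on them:

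- Define VAS time points before extubation as not assessable (not zero), and give the number assessable per arm at each time.
- Count all opioids given in the 48 h after surgery, including during ventilation, and show the total split into before and after extubation.
- Record ventilation in hours or fractional days; the data list gives days, and 12 h is half of one.

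The cost is a wording amendment, one VAS rule, one extra opioid split and one sensitivity analysis. The downsides are some additional missing early VAS values (the 6 h gap exists under the present rule too), a shorter VAS-driven period within the 48 h total for long-ventilated patients, and somewhat more variability from them.

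### Masking is stated for the statistician alone; the protocol should say whether patients and VAS scorers know the arm, because expectation can enter 48-hour MME and VAS before any analysis

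*Protocol*

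**What the plan says.** The section on randomization, allocation and blinding contains one sentence on masking: "Masking will be performed for the statistician". No other role is named as masked anywhere in the protocol. It also does not say that patients will be told their arm.

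The postoperative pain protocol, common to both arms, has two steps before morphine. First, "If VAS >4 points on the scale, patients will receive NSAIDs" (the drug named is paracetamol). Second, "If there is no effect after 30 minutes, opioid analgesics will be administered (MORPHINE 10 mg"). The second step gives no VAS value or required change, and names no one to make the judgement. Opioid dose has a daily maximum of 50 mg.

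The primary outcome is "The opioid analgesic consumption within 48 hours after surgery, calculated in milligram morphine equivalent (MME"). The first secondary endpoint is "The intensity of pain, assessed using a visual analogue scale (VAS) after extubation, 6, 12, 24, 36, 48 hours after surgery". On who gathers the data, the protocol says only: "All information will be collected by staff using paper documentation".

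The follow-up at 2 and 6 months covers chronic pain and numbness. Spirometry is repeated at 48 hours and before discharge.

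**The concern.** Expectation acts when the patient scores pain and when someone decides that paracetamol has failed. Both happen before the data reach the statistician. If patients or scorers know the arm, a difference in expectation between arms can move VAS directly, and can move MME by changing who crosses the threshold or who is judged not to have responded. The protocol accepts that psychological state matters here: depression is a non-inclusion criterion because of its effect on how pain is perceived.

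The Objectives section sets two purposes: to establish whether cryoablation has a clinically significant analgesic effect on opioid use and VAS, and to supply data for a larger trial. A difference produced by expectation would enter both. The 2- and 6-month reports of pain and numbness rest on what the patient says, and spirometry depends on effort, so the concern does not end at 48 hours.

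**Working it through.** **No figure to reproduce.** The protocol states that no sample size calculation was done. It gives no alpha, SD or effect size. The check is therefore a reading of the text, followed by an illustration on assumed values.

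**Step 1: where the arm could influence the record.**

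| Item | What the protocol fixes | Where expectation can enter |
|---|---|---|
| VAS at the scheduled times | Times only | The patient's own score; the scorer's manner of asking |
| First rescue step | Threshold VAS above 4 | The patient's own score |
| Second rescue step | 30-minute wait, 10 mg dose | The undefined judgement of no effect |
| 48-hour MME | Sum of doses | Inherited from both rescue steps |
| Analysis | Masked statistician | None, but the data are already fixed |

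A shift in reporting reaches MME only if it carries a patient across the threshold or alters the 30-minute judgement, and total dose is limited each day. The ladder therefore attenuates the bias in MME. It does nothing for VAS. Opioids given before extubation, or outside the ladder, are not driven by VAS and are not part of this point.

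**Step 2: could patients be left unaware?** Cryoablation is done before weaning from bypass, so the patient is not awake for it. The control is also an intercostal procedure, injected under the parietal pleura. Its timing is not stated. The site and the title of reference 14, which contains the word intraoperative, suggest that it too is given during the operation, but this is inference.

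**Step 3: illustration of size.** From the document: 15 per arm. Assumed: two-sided alpha 5%, SD of 15, 20 or 30 MME, no true effect, and a differential bias b in one arm.

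- Standard error = SD × √(2/15), which is 5.48, 7.30 and 10.95 MME.
- Noncentrality = b / standard error. For b = 5 MME: 0.913, 0.685 and 0.456.
- False-positive rate = P(|T| > 2.048), with T noncentral t on 28 degrees of freedom.

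| Assumed bias | SD 15 | SD 20 | SD 30 |
|---|---|---|---|
| 5 MME | 14.3% | 10.1% | 7.3% |
| 2.5 MME | 7.3% | 6.3% | 5.6% |
| 1 MME | 5.4% | 5.2% | 5.1% |

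**Step 4: check with the planned tests.** I simulated 40,000 trials per setting. Totals were normal with mean/SD 30/15, 40/20 or 50/30, rounded to 10 mg steps and limited to 0 to 100 MME (2 × 50). In one arm, each patient due any dose lost one 10 mg dose with probability p.

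| p (mean shift) | Mann-Whitney | Welch |
|---|---|---|
| 0 (none) | 4.5 to 4.7% | 4.8 to 5.0% |
| 0.1 (about 1 MME) | 4.7 to 5.0% | 5.0 to 5.3% |
| 0.25 (about 2.4 MME) | 5.3 to 6.5% | 5.6 to 6.9% |
| 0.5 (about 4.7 to 4.8 MME) | 6.8 to 12.3% | 7.3 to 13.2% |

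The last row means one dose fewer in about 7 of the 15 patients in one arm.

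Two further assumptions lie behind these figures. Morphine 10 mg is counted as 10 MME, although the route is not stated and the conversion table sets 10 mg by injection against 30 mg by mouth. The limit of 100 MME takes 48 hours as two dosing days, whereas by calendar date the window can touch three.

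**The case against.** The strongest reply is that the point argues from silence. A reader might infer that patients will be told their arm and that the trial is open-label for everyone but the statistician. The text does not say so. What stands is narrower: the section meant to settle blinding does not settle it for the two roles whose knowledge matters most. Who is masked is a design decision that belongs in the protocol, not a detail to leave to a statistical analysis plan.

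Second, the rescue ladder is the same in both arms, with a fixed threshold, paracetamol first, a fixed wait, a fixed dose and a daily maximum. This narrows staff discretion and weakens the link from reporting to MME. That stands, so it would be wrong to say that the primary outcome is unprotected. VAS has no such protection.

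Third, a reader might infer that the bias favours cryoablation, or that 7 to 14% is an estimate of this trial's error rate. Neither is supported. Both arms receive an active intercostal procedure, and the Background cites favourable studies but also a randomized study with no VAS difference. The SDs and the bias are assumed, and a bias of 5 MME is sizeable.

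Fourth, masking would be partial. The protocol itself lists paresthesia in the access area and right arm, and cryoablation also covers one space above and one below the approach, so numbness may reveal the arm. The surgeon cannot be masked. Rescue staff may be hard to mask, because only the control arm is described as receiving ropivacaine (20 ml × 7.5 mg/ml = 150 mg). All of this stands. It limits the gain but is no reason to leave the matter unstated.

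**Conclusion.** The concern holds in limited form. The protocol names the statistician as masked and is silent on patients and VAS scorers, while MME (in part) and VAS (directly) depend on what patients report after extubation. Masking the statistician cannot correct that.

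The mechanism carries the point, not the numbers. On the assumptions above, a 5 MME differential bias would raise false positives from 5% to about 7 to 14%. Half that bias gives about 6 to 7%, and 1 MME is practically nominal. Neither the size and direction of any real bias, nor the share that masking would remove, can be computed from the documents. That patients could be left unaware depends on the control block being given under anaesthesia, which the protocol does not state. For a 30-patient pilot this is a cheap improvement worth making, not a flaw that invalidates the design.

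**What to change.** First confirm, and state, whether the control block is given under anaesthesia. If it is, add to the section on randomization, allocation and blinding that:

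1. patients are not told their arm, at least through the 48-hour assessments and preferably until the 6-month follow-up, unless safety requires disclosure. The longer period also covers the patient-reported outcomes at 2 and 6 months and the pre-discharge spirometry;
2. VAS is collected, where existing staffing allows, by staff who are not told the arm;
3. for any role that is not masked (the surgeon, and possibly the staff who give rescue), the MME and VAS results are reported as open to performance and reporting bias.

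The cost is protocol wording, a change to the patient information and, where possible, an arrangement for who collects VAS. No sham procedure or larger sample is needed, and no change to any dose or rescue rule is proposed. The gain will be partial, because numbness or paresthesia may reveal the arm.

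I would not add a question asking patients to guess their arm at 48 hours, since patients with less pain may guess cryoablation because it worked. Nor would I add data fields for each rescue decision: they cannot detect bias in the patient's own report, and they are case-report-form detail.

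### Does the statement that no data were available for a sample size calculation, set beside a 'determine whether' objective and 15 patients per arm, require a change to the plan?

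*Protocol*

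**What the plan says.** The Study design section states: "A single-center pilot prospective randomized clinical trial is planned, with a 1:1 allocation ratio". Research participants gives the size: "30 patients (15 patients in each group) who are scheduled to undergo minimally invasive mitral valve surgery under cardiopulmonary bypass". Under Randomization, allocation, blinding, the only remark on how that number arose is "Sample size calculation was not performed because no data were available to estimate sample size".

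The Background refers to earlier evidence. One item begins "In 2000, a prospective randomized controlled trial was published involving 30 patients who underwent minimally invasive mitral valve surgery"; that trial also took coronary bypass patients, and its result is given only in words (less pain, less analgesic). Another, in surgical rib stabilisation, is said to have "resulted in a 25% reduction in opioid analgesics consumption" relative to an extrapleural catheter. A 2021 randomised trial is also cited, with the remark that its opioid use was not adequately assessed.

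The Objectives section has two parts. The first is "To determine whether cryoablation of intercostal nerves provides a clinically significant analgesic effect". The second is "To obtain preliminary data for planning a subsequent larger prospective randomized trial". For the primary outcome, opioid use over 48 hours in MME, the Statistical analysis section says: "Comparisons of continuous outcomes will be made using the Mann-Whitney test for non-normal variables and the Welsh t test for normal variables". It states no alpha, power, effect size or SD.

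**The concern.** Three things seem not to fit together. First, a protocol that cites randomised trials of the same technique, one of them partly in the same surgery, and also a numerical opioid effect, appears to contradict itself when it says there was nothing to size the trial from. Second, an objective to determine whether an effect is clinically significant reads as confirmatory, yet no threshold is given and 30 patients is small. Third, the planning objective needs an estimated difference and an SD, while the analysis text mentions only tests, and a Mann-Whitney p-value provides neither.

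If all of that held, a non-significant result could be misread as evidence of no worthwhile effect, a chance significant one could be taken as proof, and the larger trial could be left without usable planning figures.

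**Working it through.** **Inputs.** From the protocol: 15 per arm, 1:1 allocation, 48-hour MME as primary outcome, and a 25% reduction as the only opioid effect it quantifies. Assumed, because the protocol gives none: two-sided alpha 0.05, power 80% or 90%, and a coefficient of variation (CV = SD / control mean) between 0.3 and 1.0. There is no stated calculation to reproduce.

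**Detectable difference.** By normal approximation, (1.960 + 0.842) × √(2/15) = 2.802 × 0.365 = 1.02 SD. With the noncentral t distribution it is 1.06 SD for 80% power and 1.23 SD for 90%. For Mann-Whitney, using its relative efficiency of 0.955 under normality, it is about 1.09 SD.

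**Precision of the difference.** t(0.975, 28) × √(2/15) = 2.048 × 0.365 = 0.75 SD.

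**Power for a 25% reduction.** The standardised effect is 0.25 / CV. Power is from the t test; n per arm for 80% power is by normal approximation.

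| Assumed CV | Effect (SD) | Power, 15 per arm | n per arm for 80% |
|---|---|---|---|
| 0.3 | 0.83 | 60% | 23 |
| 0.4 | 0.63 | 38% | 41 |
| 0.5 | 0.50 | 26% | 63 |
| 0.6 | 0.42 | 20% | 91 |
| 0.8 | 0.31 | 13% | 161 |
| 1.0 | 0.25 | 10% | 252 |

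**Precision of the SD.** With 28 degrees of freedom the chi-square 95% limits are 0.79 and 1.35 times the estimate. Since sample size goes with the square of the SD, that is a (1.352 / 0.794)² = 2.9-fold range for the next trial. This limit comes from having 30 patients; rewording the protocol would not narrow it.

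**What the table shows about the supposed contradiction.** For one and the same 25% effect, the required n per arm runs from 23 to 252 depending only on the CV. A percentage reduction without an SD therefore does not size a trial. Set against that need, the Background offers:

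- the 30-patient trial: mixed mitral and coronary surgery, with no figures quoted;
- the 2021 trial: opioid use discounted by the protocol itself, and no difference on the pain scale;
- the rib-stabilisation study: a percentage only, against an extrapleural catheter, whereas the control here is a ropivacaine intercostal block;
- the systematic review of 23 studies: direction of effect and evidence grades only.

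None of these, as reported in the protocol, gives a mean or SD of 48-hour MME. The sentence about sample size is brief, but the Background does not contradict it.

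**What the analysis text commits to.** It names tests for comparisons. It does not exclude estimates, and the data list records opioid dose over 48 hours for each patient. The group means, their difference with a confidence interval, and the SD follow directly from those data.

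**The case for a change.** The strongest case for a change is that the objectives and the reason for the sample size belong in the protocol, so a statistical analysis plan cannot supply them. On this view a pilot needs no power calculation but should say why it has its size, and 30 is left without even a feasibility or precision argument. For a 25% effect, 80% power would need a CV of about 0.24 or less (0.25 / 1.06). Removing patients ventilated for more than 12 hours could reduce the analysed number: at 12 per arm the detectable difference is 1.20 SD and the half-width 0.85 SD. Recasting the objective as estimation would cost a few sentences and no patients.

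Part of this stands. The first objective gives no threshold for clinical significance and is ambitious for an unsized pilot, and the sample-size sentence would be clearer if it said which quantity was missing. But it would be too strong to say that 15 per arm cannot answer the question: a true effect above about 1.06 SD has at least 80% power, and whether that is plausible depends on an SD the document does not give. The low power figures combine a borrowed effect with assumed CVs. The feared misreading is also not built into the plan, which has no success criterion and no rule for interpreting a null result. Writing in feasibility as the reason for 30 would give a reason that the document nowhere states.

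**Conclusion.** No change to the plan follows. The arithmetic is sound: with all 30 analysed and two-sided 0.05 assumed, the trial has 80% power only for about 1.06 SD, estimates the difference to within about 0.75 SD, and fixes the SD to within 0.79 to 1.35 times its estimate. The t-based and chi-square figures also assume roughly normal data. These numbers describe the ordinary limits of a 30-patient pilot; they do not show that the plan misses a target it set, because it set none.

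The apparent contradiction goes once the sentence is read as written, since no usable mean or SD for this contrast is quoted anywhere in the protocol. Effect estimates, intervals and the SD are commonly specified in a statistical analysis plan, which is not at hand here, and any competent analyst would report them from the recorded MME. What is left is a mismatch of wording between an efficacy-style objective and a design openly labelled a pilot, with a larger trial to follow. Readers should take the efficacy result as preliminary and should not read a non-significant test as absence of effect; the design and the second objective already point that way.
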